12.3.2 Assessment of Hepatotoxicity

The number and percentage of subjects in each treatment group with maximum on-treatment laboratory values meeting the following criteria compared to the upper limit of normal (ULN) will be summarized by treatment group to assess potential hepatotoxicity.

- $ALT \geq 3 \times ULN$ and total bilirubin $\geq 2 \times ULN$
- $AST \geq 3 \times ULN$ and total bilirubin $\geq 2 \times ULN$
- ALT and $AST \geq 3 \times ULN$ and total bilirubin $\geq 2 \times ULN$
- $ALT \geq 3 \times ULN$ and total bilirubin $< 2 \times ULN$
- $AST \geq 3 \times ULN$ and total bilirubin $< 2 \times ULN$
- ALT and $AST \geq 3 \times ULN$ and total bilirubin $< 2 \times ULN$.

The maximum ratio relative to the ULN is used to determine if subjects met the criteria listed above. The ALT, AST, and total bilirubin values do not need to be concurrent in order to meet the defined criteria. For ALT, AST, and total bilirubin, a subject is counted if the post-baseline laboratory value during the Treatment Period meets the above criteria regardless of Baseline laboratory value (i.e., the post-baseline laboratory value does not need to be worse than Baseline laboratory value).

A listing of all ALT, AST, total bilirubin, and alkaline phosphatase values will be provided for each subject who met any of the criteria defined above.

12.4 Bone Mineral Density

All analyses and summaries of bone mineral density (BMD) will be performed for each segment, i.e., femoral neck, lumbar spine, and total hip. For subjects who had a right-side scan performed (rare instances), their data for right femoral neck and right femoral total hip were included in the analysis with the data for the left femoral neck and left total hip, respectively (available for the majority of subjects), and an additional analysis was performed using the left side only. If more than one scan is reported for an anatomical

segment within an analysis window, the worse (the lower value) of the multiple measurements were used for analysis for each anatomical segment.

12.4.1 BMD in the Treatment Period

BMD

A continuous summary of BMD at Baseline, Between Month 3 and Month 6, Month 6, and Final Visit will be provided by treatment group. This summary will include the mean, SD, median, minimum, maximum, and first and third quartiles. This analysis will be repeated excluding subjects who switched machine manufacturer type (Lunar or Hologic), subjects with scans only on Lunar machines, and subjects with scans only on Hologic machines.

The analysis of percent change in BMD from Baseline to each relevant visit in the Treatment Period will be performed. The mean percent change in BMD from baseline to Month 6 and Final Visit during the Treatment Period will be compared between each elagolix dose group and placebo, as well as between elagolix 300 mg BID group and elagolix 300 mg BID + E2/NETA group, using ANCOVA with treatment as the main effect and Baseline value of corresponding parameter as a covariate. This analysis will be repeated excluding subjects who switched machine manufacturer type (Lunar or Hologic), subjects with scans only on Lunar machines, and subjects with scans only on Hologic machines.

The number and percentage of subjects with percent change from Baseline to Between Month 3 and Month 6, Month 6, and Final Visit in the Treatment Period in mutually exclusive categories of BMD decrease: $\leq 0\%$, $> 0\% - \leq 1.5\%$, $>1.5\% - \leq 3\%$, $> 3\% - \leq 5\%$, $> 5\% - < 8\%$, and $\geq 8\%$ will be summarized by treatment group and comparison between each elagolix dose group and placebo, as well as between elagolix 300 mg BID group and elagolix 300 mg BID + E2/NETA group, will be made using Fisher's exact test.

Z-Score and T-Score

A continuous summary of the Z-score at Baseline, Between Month 3 and Month 6, Month 6, and Final Visit will be provided by treatment group. This summary will include the mean, SD, median, minimum, maximum, and first and third quartiles. A categorical summary of Z-score will be summarized at Baseline, Between Month 3 and Month 6, Month 6, and Final Visit for the following categories: ≤ -2.0 , > -2.0 to ≤ -1.5 , > -1.5 to ≤ -1.0 , and > -1.0 for all subjects, subjects with BMD decrease $\geq 3\%$ at Month 6, and subjects with BMD decrease $< 3\%$ at Month 6, respectively. The categorical summary of worst Z-score at any time in the Treatment Period will be produced by treatment group for each anatomical region.

A continuous summary of the T-score at Baseline, Between Month 3 and Month 6, Month 6, and Final Visit will be provided by treatment group. A categorical summary of T-score will be summarized at Baseline, Between Month 3 and Month 6, Month 6, and Final Visit for the following categories: ≤ -2.5 , > -2.5 to < -1.0 , and ≥ -1.0 for all subjects, subjects with BMD decrease $\geq 3\%$ at Month 6, and subjects with BMD decrease $< 3\%$ at Month 6, respectively. The categorical summary of worst T-score at any time in the Treatment Period will be produced by treatment group for each anatomical region.

Plots will be provided by treatment group for:

- Percent change from Baseline to Month 6 in BMD vs. Baseline BMD values;
- Percent change from Baseline to Month 6 in BMD vs. Baseline BMD values for subjects with greater than 3% BMD decrease;
- Percent change from Baseline in BMD at Month 6 vs. Baseline Z-score;
- Maximum percent change from Baseline to Post-Baseline in BMD vs. Baseline Z-score;
- Categorical summary of lumbar spine BMD percent change from Baseline to Month 6.

A plot by treatment group of the cumulative distribution function of percent change from baseline in BMD at Month 6 and the Z-scores at Month 6 will be provided. Additionally, the boxplots of Z-scores at baseline, Month 6, Post-Treatment Month 6, and Post-treatment Month 12 will be provided by treatment group. This will be repeated for T-scores.

Listings of subjects meeting the following thresholds during the treatment period will be provided:

- Listing of subjects with bone decrease $\geq 8\%$
- Listing of subjects with Z-score ≤ -1.5
- Listing of subjects with T-score ≤ -1.5
- Listing of subjects with Z-score ≤ -1.5 and bone decrease $\geq 8\%$ in the same region
- Listing of subjects with T-score ≤ -1.5 and bone decrease $\geq 8\%$ in the same region.

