8.1.5 Demographic, Baseline Characteristics and Concomitant Medications

Demographic and baseline characteristics will be summarized by treatment group.

Overall comparability among treatment groups will be performed using the following methods: a one-way analysis of variance (ANOVA) with treatment group as the main effect for continuous variables, Fisher's exact test (or its generalization to $r \times c$ tables) for qualitative categorical variables and the Cochran-Mantel-Haenszel (CMH) row mean scores test for ordered categorical variables.

Medical history will be summarized by condition/diagnosis by treatment group (no treatment group comparisons will be made). The duration of the study drug exposure will be summarized by treatment group.

Protocol deviations and reasons for discontinuation will be summarized.

Concomitant medications will be coded using the World Health Organization (WHO) dictionary and summarized with frequencies and percentages.

The baseline MBL volume will be defined as the mean of MBL volume from the qualified menstrual cycles during the Screening Period prior to the first study drug dose date, in which the total MBL volume is from all validated and non-validated sanitary products that subjects returned and where the total MBL volume of validated sanitary products only (excluding non-validated sanitary products) is greater than 80 mL. All menstrual cycles during the Screening Period in which the total MBL volume of validated sanitary products only is less than or equal to 80 mL are not qualified to be considered for baseline. The baseline for bleeding days will be based on the assessments from the qualified menstrual cycles that are used to calculate the baseline MBL volume.

The baseline values for other variables will be defined as the last non-missing assessment obtained prior to the initiation of the study drug unless otherwise specified.

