3.0 Introduction

This statistical analysis plan (SAP) describes the planned statistical analyses for elagolix (ABT-620) Study M12-815 titled "A Phase 3 Study to Evaluate the Efficacy and Safety of Elagolix in Combination with Estradiol/Norethindrone Acetate for the Management of Heavy Menstrual Bleeding Associated with Uterine Fibroids in Premenopausal Women." The analysis plan was created based on the Study Protocol M12-815 Amendment 3 dated 25 September 2017.

This analysis plan describes both the efficacy and safety analyses. The pharmacokinetic data will be analyzed separately and is not addressed in this SAP.

The SAS System 9.2 or above will be used to perform the statistical analyses. All statistical tests will be two-sided and a significance level of 0.05 will be used unless otherwise specified.

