4.3 Sample Size

Approximately 400 subjects will be randomized in a 1:1:2 ratio to placebo (N = 100), elagolix 300 mg BID (N = 100), or elagolix 300 mg BID plus E2/NETA (N = 200). The sample size will provide at least 90% power to detect a difference between the elagolix 300 mg BID plus E2/NETA group and the placebo group in the percentage of subjects with menstrual blood loss (MBL) volume < 80 mL during the Final Month (as defined in Section 7.2) and 50% or greater reduction in MBL volume from Baseline to the Final Month under the assumption of responder rates being 60% and 30% for elagolix 300 mg BID plus E2/NETA and placebo, respectively. The sample size determination is primarily driven by the need for a sufficient number of patients for the safety database. The above sample size was calculated using nQuery advisor 7.0.

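### SAP 12.4.1 tests six ordered bone-loss categories with Fisher's exact test, so a supportive safety comparison loses power against small shifts; the ANCOVA of mean change is unaffected

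*SAP*

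**What the plan says.** SAP Section 12.4.1 summarizes percent change in BMD "in mutually exclusive categories of BMD decrease": no loss, more than 0 to 1.5%, more than 1.5 to 3%, more than 3 to 5%, more than 5 to under 8%, and 8% or more. It does so for three time points: between Month 3 and Month 6, Month 6, and Final Visit. For three pairs of arms (each elagolix group against placebo, and elagolix alone against E2/NETA) the comparison with the "elagolix 300 mg BID + E2/NETA group, will be made using Fisher's exact test". No scores or trend test are given. The SAP does not say whether the test is applied to the whole 2 x 6 table or to one category at a time.

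The same section compares mean percent change by ANCOVA for the same three pairs, at Month 6 and Final Visit. Protocol Section 8.1.8.4 adds an ANCOVA on data pooled from the two pivotal studies. It also promises a comparison of BMD categories, with cumulative cut-offs of -3%, -5% and -8% as examples, but names no test for them.

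SAP Section 12.1 gives Fisher's exact test to qualitative categorical variables. Protocol Section 8.1.5, for baseline comparability only, uses "the Cochran-Mantel-Haenszel (CMH) row mean scores test for ordered categorical variables".

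**The concern.** The six categories are graded amounts of bone loss, but Fisher's test on a 2 x 6 table would return the same p-value if the columns were shuffled. It spreads its sensitivity over every kind of difference, so it is weak against the one that matters most here, a general move toward greater loss. If it is applied category by category, a middle category can stay almost unchanged while the whole distribution moves through it.

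BMD is named in the second study objective. Any residual loss on E2/NETA relative to placebo is likely to be small, since Phase 2b gave a lumbar spine mean of -0.1% on that regimen (Protocol Section 3.2.2). Small shifts are where ignoring the order costs most, and a non-significant categorical result could be read as reassurance.

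**Working it through.** **The plan's own figure.** The documents state no power for any BMD comparison. The only stated power is for the primary endpoint: "The sample size will provide at least 90% power to detect a difference", with responder rates of 60% and 30% in 200 and 100 women.
- Pooled rate = (100 x 0.30 + 200 x 0.60)/300 = 0.50.
- Null SE = sqrt(0.25 x (1/100 + 1/200)) = 0.0612.
- Alternative SE = sqrt(0.21/100 + 0.24/200) = 0.0574.
- z = (0.30 - 1.96 x 0.0612)/0.0574 = 3.13, so power is 99.9%. The statement holds, but it says nothing about BMD.

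**Inputs from the documents.** Two-sided alpha 0.05 (SAP Section 3.0); 100 placebo and 200 E2/NETA (SAP Section 4.3); the six categories (SAP Section 12.4.1).

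**Spread, inferred from Phase 2b (Protocol Section 3.2.2).** For a normal distribution, SD = (cut - mean)/z(proportion beyond the cut).
- E2/NETA, mean -0.1%: 10.2% lost 3% or more (8.2 + 2), so (-3 + 0.1)/(-1.27) = 2.3. For 2% losing 5% or more, (-5 + 0.1)/(-2.05) = 2.4.
- Elagolix alone, mean given as both -3.6% and -3.8%: 33% lost more than 5% (25 + 8) and 8% lost 8% or more, which give 2.7 to 3.2. The 3% cut lies too close to the mean to give a usable SD.

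**Assumed.** Normal changes, placebo mean 0, SD 2.4 to 3.0, shifts up to 1.5 points, 75% or 100% of women with a Month 6 scan, and Fisher's test on the whole table.

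**Method.** 1,500 simulated trials per setting (simulation error at most sqrt(0.25/1500) = 1.3 points). Values were cut into the six categories. Three tests were run: Fisher's test on the 2 x 6 table (999 Monte Carlo tables); a row mean scores test with rank scores, equivalent to the tie-corrected Wilcoxon test; and a t-test on the uncut values, standing in for the ANCOVA.

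Power in %, placebo against E2/NETA:

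| Scanned | SD | Shift (points) | Fisher | Ordinal | Uncut values | Fisher/ordinal |
|---|---|---|---|---|---|---|
| 100 v 200 | 2.4 | 0.5 | 17 | 32 | 41 | 0.52 |
| | | 0.75 | 40 | 65 | 73 | 0.63 |
| | | 1.0 | 66 | 87 | 92 | 0.75 |
| | | 1.5 | 97 | 100 | 100 | 0.97 |
| 100 v 200 | 3.0 | 0.5 | 10 | 24 | 30 | 0.43 |
| | | 0.75 | 23 | 43 | 53 | 0.52 |
| | | 1.0 | 43 | 69 | 78 | 0.62 |
| | | 1.5 | 81 | 96 | 98 | 0.84 |
| 75 v 150 | 2.4 | 0.5 | 14 | 27 | 31 | 0.51 |
| | | 1.0 | 51 | 77 | 84 | 0.66 |
| | | 1.5 | 89 | 98 | 99 | 0.91 |
| 75 v 150 | 3.0 | 0.5 | 8 | 18 | 22 | 0.48 |
| | | 1.0 | 29 | 57 | 65 | 0.51 |
| | | 1.5 | 66 | 91 | 94 | 0.73 |

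With no shift, all three tests reject about 5% of the time; at 0.1 points they do little more. With elagolix alone at -3.6% (SD 3.2), against placebo or against E2/NETA, every test has about 100% power.

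**Choice of scores.** At 75 v 150, SD 2.7 and a shift of 0.8 points, Fisher has about 22%, rank scores 44% and integer scores (1 to 6) 43%. Now suppose that 8% of E2/NETA women lose bone rapidly (mean -8, SD 1.5) and the rest match placebo (SD 2.4; 100 v 200). Fisher has 39%, rank scores 18%, integer scores 39%, and a test of the cumulative 5% cut-off 74%.

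**Category by category.** Take elagolix alone at mean -3.6 and SD 3.0, against placebo with SD 2.4, 100 per arm. The 1.5 to 3% category holds Phi(0.70) - Phi(0.20) = 18% against Phi(-0.625) - Phi(-1.25) = 16%. Fisher's test on that category is significant about 3% of the time, despite a mean loss of 3.6 points.

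**The case against.** The strongest reply is that the plan already has a better test. The ANCOVA uses the uncut values, covers the same three pairs, and in the table above beats the ordinal test wherever there is a shift and room to gain. Per-category counts, cumulative distribution plots and listings of losses of 8% or more will show a shift whatever the categorical p-value is. The BMD p-values are outside the ranked endpoints and carry no decision rule. All of this stands. A reader might infer that the trial has only half the power to show bone loss, or that the comparison of E2/NETA with elagolix alone is compromised; the documents support neither.

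A second reply is that no protocol rule is broken. That also stands: the row mean scores test is named for baseline comparability only, and Protocol Section 8.1.8.4 leaves the details to the SAP. The most that can be said is that Fisher's test fits poorly with the plan's own distinction between qualitative and ordered variables.

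A third reply is that categories are useful because they can reveal a minority with large losses, and that a rank test would blunt this. It is correct about rank scores (18% against 39% above), so a plain switch to Wilcoxon would have a real cost. It does not apply to integer scores, which matched Fisher's test in that scenario.

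The ANCOVA leaves one gap. For the window between Month 3 and Month 6, the SAP names no between-group test other than Fisher's. The gap is modest. Scans are scheduled at Month 6 or at premature discontinuation, and the earliest on-schedule Month 6 scan falls on about Day 168 - 15 = 153, after the window closes at Day 140. The window therefore holds mainly women who stopped early, and a last scan there also counts at Final Visit, which the ANCOVA covers.

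**Conclusion.** The point holds as a defect in a supportive analysis. For shifts of about 0.5 to 0.8 points between E2/NETA and placebo, Fisher's test on the six categories has roughly half to two-thirds the power of an ordinal test (ratios of 0.43 to 0.63 at 0.5 to 0.75 points). The ratio is 0.51 to 0.75 at 1.0 point and 0.73 to 0.97 at 1.5 points, and nothing is lost at the Phase 2b effect of elagolix alone. Half the power is therefore not a general figure: it belongs to small shifts, where the ordinal test itself has only about 18% to 65% power.

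The sizes rest on normal changes, a placebo mean of zero, the assumed SDs, shifts and scan rates, and a whole-table test. The shifts are not taken from the documents. The direction, that ignoring the order loses power against a shift, does not depend on the exact values. Integer scores were checked against a rapid-loser pattern in one scenario only.

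**What to change.** In SAP Section 12.4.1, for each planned pair of arms, compare the six categories with the CMH row mean scores test using integer table scores, and say that it is applied to the whole table. Specify table scores explicitly, because rank scores lose sensitivity to a minority with large loss.

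Add Fisher tests or confidence intervals for the proportions at or beyond the cumulative cut-offs in Protocol Section 8.1.8.4 (-3%, -5%, -8%). Derive these from the measured percent change, since the SAP's categories put losses of exactly 3% and 5% on the milder side of the cut. State that the ANCOVA remains the main between-group analysis of BMD.

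The cost is a change of wording, one procedure option and slightly more output; data collection does not change. The ordered hemoglobin-change categories in SAP Section 11.3.4 could be treated the same way. That is optional: the effect there was not quantified, and hemoglobin change has its own ANCOVA.

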12.4.2 BMD in the Post-Treatment Follow-Up Period

For subjects who do not enter the extension study, percent change from Baseline to Post-Treatment Follow-up Month 6, Post-Treatment Follow-up Months 7 – 11, and Post-Treatment Follow-up Month 12 will be summarized for each treatment group with descriptive statistics. There will be no statistical testing of Post-Treatment Follow-up BMD values.

The analysis of percent change in BMD will be repeated to include only the subset of subjects who had a Treatment Month 6 and a Post-Treatment Follow-up Month 6 scan. Similarly, this analysis will be repeated to include only the subset of subjects who had a Treatment Month 6 and a Post-Treatment Follow-up Month 12 scan.

Percent change from Baseline in BMD to each of the Post-Treatment visits will be summarized for each treatment group with frequencies and percentage for categories of

BMD decrease: $\leq 0\%$, $> 0\% - \leq 1.5\%$, $>1.5\% - \leq 3\%$, $> 3\% - \leq 5\%$, $> 5\% - < 8\%$, and $\geq 8\%$.

Cross-tabulations of the number and percentage of subjects in each of the previously noted categories of percent change from Baseline for the following:

- Treatment Month 6 to Post-Treatment Follow-up Month 6
- Treatment Month 6 to Post-Treatment Follow-up Month 12
- Final Treatment to Post-Treatment Follow-up Month 6
- Final Treatment to Post-Treatment Follow-up Month 12
- Post-Treatment Follow-up Month 6 to Post-Treatment Follow-up Month 12.

The subjects included in these analyses will be limited to those who had values at these time points.

As described above for the Treatment Period, continuous and categorical summaries of the Z-score and T-score at each time point during the Post-Treatment Follow-up Period will be provided.

Listings of subjects meeting the following thresholds during the Post-Treatment Follow-up period will be provided:

- Listing of subjects with bone decrease $\geq 3\%$ and T-score < -1.0 in the same region
- Listing of subjects with T-score ≤ -1.5 .

12.5 Vital Signs and Body Weight

Vital sign variables include pulse rate, sitting systolic blood pressure, sitting diastolic blood pressure, and oral body temperature.

Vital sign variables will be summarized with mean, median, standard deviation, minimum, and maximum by treatment group.

Analyses of mean change from Baseline to each relevant visit during the Treatment Period in vital sign variables and weight will be performed. The mean change from Baseline to each relevant visit in the Treatment Period will be compared between each elagolix dose group and placebo using one-way ANOVA with treatment as the main effect.

The number and percentage of subjects who have PCS vital sign and weight values meeting the following criteria will be summarized by treatment group. All increase/decrease is calculated from Baseline to a post-baseline visit in the Treatment Period.

The number and percentage of subjects who have a sustained PCS vital sign value and a listing of these subjects will be provided. A sustained PCS value is defined as 3 consecutive PCS values in the Treatment Period.

- Diastolic blood pressure
 - ≤ 50 mmHg and ≥ 15 mmHg decrease
 - > 90 mmHg and ≥ 15 mmHg increase
 - ≥ 100 mmHg
- Systolic blood pressure
 - ≤ 90 mmHg and ≥ 20 mmHg decrease
 - ≥ 140 mmHg and ≥ 20 mmHg increase
 - ≥ 160 mmHg
- Pulse rate
 - ≤ 45 bpm and ≥ 15 bpm decrease
 - > 100 bpm and ≥ 15 bpm increase
 - ≥ 120 bpm
- Weight
 - $\geq 5\%$ decrease
 - $\geq 7\%$ increase.

Change in vital signs from Baseline to relevant Post-Treatment Follow-up visit(s) (Post-Treatment Month 1, Month 3, Month 6, Month 9, Month 12, and Final Visit) will be summarized by treatment group with descriptive statistics.

12.6 Endometrial Biopsy

The number and percentage of subjects in each category of endometrial biopsy results will be summarized at Baseline, Between Month 3 and Month 6, and Month 6 for each treatment group.

12.7 Pelvic Ultrasound and MRI

Analyses will be conducted separately for results obtained from TAU/TVU and MRI. The actual values and the change from Baseline to Month 3 (TAU/TVU only), Month 6, Follow-up Month 3 (TAU/TVU only), and Follow-up Month 6 will be summarized by treatment group with descriptive statistics.

12.7.1 Ovarian Cysts

The presence of ovarian cysts will be noted at Baseline and each relevant post-baseline visit in the Treatment Period and Post-Treatment Follow-up Period. Significant ovarian findings include complex ovarian cyst > 3.5 cm or simple ovarian cyst > 5 cm. The number and percentage of subjects with the pre-defined complex ovarian cysts and simple ovarian cysts will be summarized for each treatment group at each relevant visit in the Treatment Period.

For each TVU/TAU or MRI assessment, information for significant ovarian findings from the cysts assessment may be available for more than one cyst at more than one ovary location (left and/or right). For such assessments, the worst assessment based on the greatest of the three dimensions across the multiple cysts at the left and/or right ovary location within the same cyst type (i.e., simple or complex) will be included in the analyses/summary. Additionally, the subject with multiple cyst findings will be counted once in the numerator and denominator when reporting the number and percentage of subjects in the relevant category of significant ovarian findings. A listing will include all

results across multiple cysts findings from multiple assessments (where available) from subjects who have significant ovarian findings.

